## **12. 2** Definitions for SLL with radiographically measurable lesions

- **Measurable disease**: the presence of at least one measurable lesion. If the measurable disease is restricted to a solitary lesion, its neoplastic nature should be confirmed by cytology/histology.
- **Measurable lesions** defined as those that can be accurately measured in at least one dimension (longest diameter to be recorded) as >20 mm with conventional techniques (PET, CT,) or as >10 mm with spiral CT scan. All tumor measurements must be recorded in millimeters (or decimal fractions of centimeters).
- Non-measurable lesions all other lesions, including small lesions (longest diameter <20 mm with conventional techniques or <10 mm with spiral CT scan), i.e., bone lesions, leptomeningeal disease, ascites, pleural/pericardial effusion, inflammatory breast disease, lymphangitis cutis/pulmonis, cystic lesions, and also abdominal masses that are not confirmed and followed by imaging techniques.
- **Baseline documentation of "Target" lesions** all measurable lesions up to a maximum of five lesions per organ and 10 lesions in total, representative of all involved organs should be identified as target lesions and recorded and measured at baseline. Target lesions should be selected on the basis of their size (determining the product obtained from the longest diameter of two perpendicular measurements) and their suitability for accurate repeated measurements (either by imaging techniques or clinically). A sum of the products of the longest perpendicular dimensions (LD) for all target lesions will be calculated and reported as the baseline sum LD. The baseline sum LD will be used as reference by which to characterize the objective tumor response.
- Non-target lesions All other lesions (or sites of disease) should be identified as

non-target lesions and should also be recorded at baseline. Non-target lesions include measurable lesions that exceed the maximum numbers per organ or total of all involved organs as well as non-measurable lesions. Measurements of these lesions are not required, but the presence or absence of each should be noted throughout follow-up.

#### **12.3** Response Criteria for SLL; based on Cheson criteria (108)

The criteria for NHL are as follows (GTD = Greatest Transverse Diameter; SPD = Sum of the Products of the Greatest Diameter):

#### **Complete Remission (CR):**

- Disappearance of all evidence of disease.
- No disease related symptoms.
- Lymph nodes, nodal masses regressed to "normal" size:
  - If >1.5 cm before treatment, regressed to  $\leq$  1.5 cm in GTD.
  - If 1.1 to 1.5 cm before treatment, regressed to  $\leq$  1 cm in GTD (or >75% in SPD). If PET scan was positive before therapy, a post-treatment residual mass of any size is permitted as long as it is PET negative.
- Spleen and all previously enlarged organs decreased to normal in size.
- If the Bone marrow was involved prior to treatment, it is clear on repeat aspirate and biopsy at the same site.

#### **Partial Remission (PR)**

- $\geq$  50% decrease in SPD of six largest dominant nodes/nodal masses.
- No increase in size of other nodes, liver or spleen.
- Splenic and hepatic nodes regressed at least 50% in SPD
- No new sites of disease.
- If the PET scan was positive before therapy, the post-treatment PET is positive in at least one previously involved site.
- Patients who achieve a CR by the above criteria, but who have persistent bone marrow involvement (or those in whom pre-treatment bone marrow was involved and post-treatment bone marrow involvement was not assessed).

#### **Relapsed Disease (RD)**

- In patients previously CR or CRu:
- New lesion > 1.5 cm in any axis
- Size of previously involved site has increase  $\geq 50\%$  in GTD.
- $\geq 50\%$  in either:
  - GTD of any previously identified node that was >1 cm in its short axis, or
  - SPD of any node or other lesion.

#### **Stable Disease (SD)**

• Patients who have achieved less than a partial remission but who have not

developed findings consistent with progressive disease.

#### **Progressive Disease (PD)**

- In patients previously PR or SD.
- $\geq 50\%$  increase from nadir or baseline in SPD or any node or lesion
- $\geq$  50% increase from nadir in GTD of any node previously >1cm in shortest diameter
- Appearance of any new lesion during or at the end of therapy.

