#### 4.1 Inclusion Criteria

Patients must meet all of the following inclusion criteria to be eligible for enrollment:

4.1.1 Have a diagnosis of CLL based on peripheral blood flow cytometry and/or bone marrow aspiration and biopsy OR diagnosis of SLL based on lymph node or bone marrow biopsy. Patients with SLL need to have measurable disease (see section 12.2 for definition of measurable disease)

4.1.2 Subject, age  $\geq$  18 years (children are excluded from this study as CLL/SLL being exceptionally rare)

- 4.1.3 Performance Status (ECOG) 0-2 (see appendix A) ECOG PS = \_\_\_\_\_ Date: \_\_\_\_\_
  - \_\_\_\_\_\_ 4.1.4 Patients must have not received any prior treatment for CLL or SLL.

	4.1.6 Adequat	e bone marrow, rena	l, and hepatic function, per local reference
lat	ooratory ranges as fol	lows:	
	4.1.6.1 Absolute	e neutrophil count (A	NC) ≥ 1,500/mm3
	A	ANC=	Date:
	4.1.6.2 Platelet of	$count \ge 100,000/mm$	3
	P	latelets=	Date:
	4.1.6.3 Hemoglo	bin > 10 g/dL	
	Hinde Intensity.	Iemoglobin=	Date:
	4.1.6.4 Serum ci	reatinine $\leq 2.0$ g/dL	or calculated creatinine clearance
	(	$(CrCl) \ge 60mL/min$	Cockcroft-Gault method)
	C	Crcl =	Date:
			Date
	4.1.6.5 AST and	$ALT \le 2.5 \text{ x institu}$	tional upper limit of normal
	(	ULN) NST-	Date
	r A	AST= ALT=	Date:
	4.1.6.6 Bilirubir	n < 2.0  x ULN, unles	s subject has Gilbert's disease
	E	siiiruoin=	Date:
	4.1.6.7 Calcium	<10.1 mg/dL (corre	cted to serum albumin as follows:
	Corrected Calcin	um = (0.8 x (4 - patie))	ent albumin)) + serum Ca
	Corrected calciu	ım= Da	ite:
4.	1.7 Females will be	either postmenopau	sal for at least 1 year or surgically sterile
for	r at least 3 months (	OR Females of child	1-bearing potential must have a negative
pr	egnancy test at scre	ening and agree to	take appropriate precautions to avoid
pro	egnancy (double bar	rier method of birt	h control or abstinence) from screening
tin	ough 5 months arter	the last dose of freat	nent
4.1	1.8 Able to compreh	nend and willing to s	ign an Informed Consent Form (ICF)
4.1	1.9 Subjects must be	e off any steroids 7 c	ays prior to the initiation of treatment.
4.1	1.10 Subjects must be	e off any curcumin,	tumeric, or vitamin D supplements for 14
	days prior to the	initiation of treatme	nt.
4	1.11 Subjects must be	able to take oral me	dications
CASE 5913		20 of 7	4

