10.1.2 Rationale for Analysis

We plan to assess VDR at baseline and on D8, after 1 week of treatment with curcumin, and prior to starting vitamin D3 treatment to prove this. Quantitative intracellular measurement of VDR by flow cytometry, in peripheral blood mononuclear cells, has been performed, and validated, by other investigators before (86). The purpose of this analysis is exploratory/proof of concept. Subjects with SLL with no peripheral blood lymphocytosis will be excluded from this analysis.

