## 11.0 STUDY PARAMETERS AND CALENDAR

#### 11.1 **Study Parameters**

#### 11.1.1 Screening Evaluation

Screening studies and evaluations will be used to determine the eligibility of each subject for study inclusion. All evaluations must be completed  $\leq$  30 days prior to administration of protocol therapy. Bone marrow biopsy, flow cytometry, cytoegenetics, and interphase FISH performed up to 5 years prior to enrollment are acceptable.

- Informed Consent
- Demographics
- Medical History
- Complete physical examination including lymph node measurements (all palpable lymph nodes will be measured in greatest dimension and documented)
- Height
- Weight
- Vital signs including: blood pressure, pulse, temperature, and respiratory rate
- Concomitant Medications Assessment including prescription medications, OTC, and nutritional/herbal supplements.
- ECOG Performance status  $\leq 2$
- Baseline Symptoms Assessment
- Laboratory Studies:

- Complete Blood Count (CBC) with differential and platelets. Absolute lymphocyte count (ALC) will be calculated from CBC and differential
- Serum Chemistries: albumin, alkaline phosphatase, total bilirubin, bicarbonate, BUN, calcium, chloride, creatinine, glucose, potassium, total protein, SGOT [AST], SGPT [ALT], sodium
- Vitamin D 25(OH) level; standard of care test (63).
- Calculated creatinine clearance will be done if creatinine and/or BUN are abnormal.
- ß-HCG for women of childbearing potential
- CT scan of chest, abdomen, and pelvis (with and without contrast) will be performed in subjects with SLL who don't have ALC<5000 and non-measurable peripheral adenopathy. MRI may be performed if subject has allergy to iodinated contrast media
- Bone Marrow Biopsy is **optional** and not required prior to enrollment in study
- Peripheral blood flow cytometry (unless already performed on bone marrow biopsy)
- Peripheral blood cytogenetics including interphase FISH analysis for chromosome 11, 12, 13, and 17 abnormalities (unless already performed on bone marrow biopsy)

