## 11.2 Calendar

Screening studies will studies are to be conducted within 30 days prior to administration of protocol therapy. Exception: Bone marrow biopsy, flow cytometry, cytometry, cytoegenetics, and interphase FISH performed up to 5 years prior to enrollment

Study Days	Pre- Study	Cycle 1 Day 1 b	Cycle 1 Day 8	Cycle 2 Day 1	Cycles 3- 6 Day 1	Cycles 7+ Day 1 f	End of Treatment	30 Day Follow Up i	Long term Follow- Up g,i
REQUIRED ASSESSMENTS									

r				1	1				
Informed Consent	Х								
Demographics	Х								
Medical History	Х								
Height	Х								
Weight	Х	Х	Х	Х	Х	Х	Х	Х	Х
Vitals (blood pressure,	Х	Х	Х	Х	Х	Х	Х	Х	Х
pulse, temperature, and									
respiratory rate)									
Physical Examination i	Х	Х		X	Х	Х	Х	Х	Х
Concomitant	Х	X		X	X	Х	Х	Х	
Medication									
Assessment									
ECOG PS	Х	X	X	X	X	Х	Х	Х	Х
Baseline Symptoms	Х	X							
Adverse Event			X	X	X	X	X	X	X
Assessment									
Peripheral blood flow	X								
cvtometry									
Peripheral blood	X								
cytogenetics and FISH									
CBC / diff / platelets i	X	X	X	X	X	X	X	X	Х
Serum Chemistry a, i	X	X	X	X	X	X	X	X	X
B-HCG women of	X	X					X		
childbearing potential									
Vitamin D 25(OH)	X	X*		X*	X*	X*	X*	X	
level									
DISEASE									
ASSESSMENT									
Lymph node	Х	X		X	X	Х	Х	Х	Х
measurement									
СТ	Х				Х				
chest/abdomen/pelvis c									
Bone marrow biopsy	Х								
(optional)									
MISC ITEMS									
Pill Diary		Х		X	X	X	Х		
TREATMENT									
Curcumin									
Vitamin D3									
CORRELATIVE									
STUDIES									
Pharmacokinetic		X	X	X					
Sampling d									
Flow cytometry e		Х	Х	X					
Ouality of life	X h	1		1	1	1	X h		
questionnaire									

**a:** Albumin, alkaline phosphatase, total bilirubin, bicarbonate, BUN, calcium, chloride, creatinine, glucose, potassium, total protein, SGOT [AST], SGPT [ALT], sodium. Calculated creatinine clearance will be done if creatinine and/or BUN are abnormal. **[UH: Order COMP2]** 

**b:** Cycle 1, Day 1 evaluations do not need to be repeated if screening evaluations were conducted within 2 weeks prior to administration of protocol therapy

c: In subjects with SLL who have ALC<5000 and non-measurable peripheral adenopathy

**d:** Plasma level of curcumin and vitamin D 25(OH)

e: For vitamin D receptor, NF-κB, and bcl-2, CLL patients only

f: For patients attaining a partial response or better

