- > 50% increase in the size of the liver and/or spleen as determined by measurement below the respective costal margin; appearance of palpable hepatomegaly or splenomegaly, which was not previously present.
- >50% increase in the absolute number of circulating lymphocytes to at least  $5,000/\mu$ L.
- Transformation to a more aggressive histology (i.e., Richter's syndrome or prolymphocytic leukemia with > 55% prolymphocytes).
- Patients not fulfilling the above criteria for progressive disease but demonstrating a decrease in hemoglobin > 2 gm/dl, decrease > 50% in platelet or granulocyte count will not be rated as progressive disease because these may occur as both a consequence of therapy and of underlying CLL. A bone marrow biopsy in such settings is strongly encouraged.

**Stable Disease** includes patients who do not fulfill the criteria for complete or partial response as defined above but do not exhibit progressive disease will be considered as having stable disease.

Parameter	CR*	PR*	PD*
Group A			
Lymphadenopathy†	None > 1.5 cm	Decrease ≥ 50%	Increase ≥ 50%
Hepatomegaly	None	Decrease ≥ 50%	Increase ≥ 50%
Splenomegaly	None	Decrease ≥ 50%	Increase ≥ 50%
Blood lymphocytes	< 4000/µL	Decrease ≥ 50% from baseline	Increase ≥ 50% over baseline
Marrow‡	Normocellular, < 30% lymphocytes, no B-lymphoid nodules. Hypocellular marrow defines CRi (5.1.6).	50% reduction in marrow infiltrate, or B-lymphoid nodules	
Group B			
Platelet count	$> 100 \ 000/\mu L$	$>100~000/\mu L$ or increase $\geq 50\%$ over baseline	Decrease of ≥ 50% from baseline secondary to CLL
Hemoglobin	> 11.0 g/dL	$>$ 11 g/dL or increase $\geq$ 50% over baseline	Decrease of > 2 g/dL from baseline secondary to CLL
Neutrophils‡	> 1500/µL	> 1500/µL or $>$ 50% improvement over baseline	

Group A criteria define the tumor load, group B criteria define the function of the hematopoietic system (or marrow).

\*CR (complete remission): all of the criteria have to be met, and patients have to lack disease-related constitutional symptoms; PR (partial remission): at least two of the criteria of group A plus one of the criteria of group B have to be met; SD is absence of progressive disease (PD) and failure to achieve at least a PR; PD: at least one of the above criteria of group A or group B has to be met.

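### The SLL criteria in 12.3 cannot register progression in the blood, although some SLL patients are foreseen with ALC of 5,000/µL or more, so pooled PFS can be overstated

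*Combined protocol and SAP*

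**What the plan says.** **Which criteria apply.** Sections 2.1 and 14.1 assign the NCI-WG criteria (12.1) to CLL and the Cheson criteria (12.3) to SLL.

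**Who is CLL and who is SLL.** Section 4.1.1 admits a "diagnosis of CLL based on peripheral blood flow cytometry and/or bone marrow aspiration and biopsy" or a "diagnosis of SLL based on lymph node or bone marrow biopsy". SLL must also have measurable disease. Neither definition carries an ALC limit.

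**Progression.** In 12.1 any one listed event is enough. The list includes a rise of more than 50% ("increase in the absolute number of circulating lymphocytes to at least" 5,000/µL) and transformation to a more aggressive histology. In 12.3 the PD list is a 50% "increase from nadir or baseline in SPD or any node or lesion", a 50% growth in the diameter of a node, or a new lesion.

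**Biologic response.** Section 12.4 covers both CLL and SLL. It credits a sustained ALC fall of more than 20%, or a fall of at least 30% in all palpable nodes. Section 14.1 puts biologic response into the primary endpoint.

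**SLL and the blood count.** Note c of the 11.2 calendar schedules CT "In subjects with SLL who have ALC<5000 and non-measurable peripheral adenopathy". Section 10.1.2 says of the flow study: "Subjects with SLL with no peripheral blood lymphocytosis will be excluded from this analysis".

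**The concern.** The protocol treats the lymphocyte count as a measure of disease in SLL when it falls, but has no place for it when it rises. Under note c, an SLL patient with ALC of 5,000/µL or more has no scheduled CT, so follow-up rests on palpation and the CBC. Section 12.3 then cannot use the CBC.

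The main stake is PFS. Section 12.6 pools CLL and SLL progression into one endpoint, but the event is defined differently in the two groups. An SLL patient whose disease advances only in the blood, or who transforms without nodal growth or a new lesion, has no PFS event. A second stake is the response rating itself, since identical data can be PR under one section and PD under the other.

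**Working it through.** **1. Assignment and label.** Sections 2.1 and 14.1 settle the criteria once the label is known. Section 4.1.1 does not settle the label for every patient. A marrow biopsy can support either diagnosis, and a patient with positive blood flow cytometry and a positive node biopsy meets both.

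**2. Are SLL patients with ALC of 5,000/µL or more foreseen?** Note c selects SLL with ALC below 5,000. Sections 11.1.1 and 11.1.2 word the CT condition the other way ("subjects with SLL who don't have ALC<5000 and non-measurable peripheral adenopathy"). The Amendment 4 entry describes the note c wording as the correct one. Either wording uses 5,000 to separate SLL patients, which has a purpose only if some lie on each side. Section 10.1.2 likewise excludes only SLL without lymphocytosis. This is an inference from the text, not a statement in it.

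**3. Thresholds for an assumed SLL patient with baseline ALC 12,000/µL.**
- Biologic response by ALC (12.4): below 12,000 × 0.80 = 9,600, sustained for 2 months.
- PD by ALC (12.1): above 12,000 × 1.50 = 18,000, which also exceeds 5,000.
- PD by ALC (12.3): no value qualifies.

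**4. Two assumed courses, with no new lesion and no growth elsewhere.**

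| Course | Change in ALC | 12.1 | 12.3 |
|---|---|---|---|
| Nodes −55%, ALC 12,000 to 19,200 | 19,200/12,000 = 1.60, +60% | PD | PR |
| Nodes stable, ALC 12,000 to 30,000 | 30,000/12,000 = 2.50, +150% | PD | SD |

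**5. Direction of the effect on PFS.** Let T be the time to nodal or lesion progression or death, and B the time to the 12.1 blood rise or transformation. The present SLL rule uses T; with the blood and transformation items it would be min(T, B), which is never later than T. The omission can only lengthen SLL PFS or leave it unchanged. It lengthens it only where B comes before T.

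**6. Effect on the primary count.** The plan gives no figure for this issue, and its design figures reproduce. With stage 1 stopping at 1 or fewer of 10 and a final limit of 5 of 29:
- Early termination at p = 0.1: 0.9^10 + 10 × 0.1 × 0.9^9 = 0.736 (stated 0.74).
- Probability of success = Σ over x = 2 to 10 of P(X = x) × P(Y ≥ 6 − x), with X ~ Bin(10, p) and Y ~ Bin(19, p). This is 0.047 at p = 0.1 (limit 0.05) and 0.805 at p = 0.3 (stated 0.8).

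In the first course, 12.3 gives a responder. Under 12.1 the patient is PD but may still meet 12.4 if all palpable nodes fell by at least 30%. Section 14.4.2 calls PD a treatment failure but has no biologic-response category, so it does not say which prevails. In the second course the patient is a non-responder either way.

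For scale only, and as an assumption: if the choice of criteria added 0, 1 or 2 responders per 29 to a true rate of 0.1 (0.100, 0.134, 0.169), the chance of declaring success would be 0.047, 0.142 or 0.284. Nothing in the documents indicates that any such shift occurs.

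**The case against.** Several stronger readings are tempting, and the documents do not support them.

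- *That nothing decides which section applies, or that the label could be chosen once results are known.* Sections 2.1 and 14.1 assign by diagnosis. The label is already needed for the SLL measurable-disease condition on the signed checklist, for screening CT and for the CLL-only flow studies on Cycle 1 Day 1. No text permits relabelling. What stands is the overlap in 4.1.1.
- *That SLL response ignores the blood.* This is true of the PR and PD lists in 12.3, but not of the primary endpoint, because 12.4 uses ALC in SLL. The 12.3 CR also asks that all evidence of disease be gone.
- *That PFS is wrong for every SLL patient whose ALC rises.* It changes only when the rise precedes other progression or death. PFS is a secondary, single-arm estimate with no stated hypothesis test.
- *That one patient could reverse the trial's conclusion.* That is so at any Simon boundary and says nothing about this defect.

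The inference that such SLL patients exist is also weaker than it looks. The CT condition is worded in opposite ways, and 11.1.2 and calendar note e limit the flow studies to CLL.

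Finally, 12.3 follows a cited standard. Following it is defensible in itself, but it does not explain why this protocol counts the blood in one direction only. Treating blood as a non-target site does not help either, since 12.2 asks only for the presence or absence of non-target lesions and gives no growth threshold.

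**Conclusion.** The point stands in a limited form. For SLL with ALC of 5,000/µL or more, a fall in ALC can count as response while a rise can never count as progression, and identical data can be PD under 12.1 and PR under 12.3. The clear effect is on PD and PFS: pooled PFS can be overstated and cannot be understated by this omission. Its size cannot be given, because the documents state neither the number of SLL patients nor how many have such counts. The effect on the primary responder count is possible but unresolved, for want of a rule on PD against biologic response. The conclusion rests on the inference that such patients were enrolled, and the remark about CT rests on note c. This is a cheap improvement to the analysis rules, not a fault in the sample size.

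**What to change.** Section 10.5 records that accrual closed on 4/12/2016, so a rule locked at registration is no longer possible. An analysis rule is. Derive the criteria set mechanically from the recorded diagnosis and baseline ALC, without reference to outcome:

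1. Rate CLL by 12.1 whatever the ALC. Rate SLL with baseline ALC of 5,000/µL or more by 12.1, and SLL with ALC below 5,000/µL by 12.3. The overlap in 4.1.1 then makes no difference to the criteria used at 5,000 or above; below that, the recorded diagnosis decides.
2. For response and PFS analysis in SLL, count as progression an ALC rise of more than 50% to at least 5,000/µL, or documented transformation.
3. State whether PD overrides biologic response in the primary count.
4. Report response and PFS under 12.3 as written for all SLL patients, as a sensitivity analysis.

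The cost is wording and a re-derivation, since the calendar already has a CBC with differential at every visit. The downside is a slight departure from the cited SLL criteria and possibly a few more progression events. SLL patients moved to 12.1 are also held to its PR conditions, which the sensitivity analysis will show.

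Sections 6.0 and 6.3 tie PR to extended treatment and progression to stopping. The sponsor must reconcile those passages with the two sets of criteria; no clinical rule is proposed here.

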#### **Evaluation of best overall response**

The best overall response is the best response recorded from the start of the treatment until disease progression/recurrence (taking as reference for progressive disease the smallest measurements recorded since the treatment started). The patient's best response assignment will depend on the achievement of both measurement and confirmation criteria.

Target	Non-Target	New	Overall
Lesions	Lesions	Lesions	Response
CR	CR	No	CR
CR	Incomplete response/S D	No	PR
PR	Non-PD	No	PR
SD	Non-PD	No	SD
PD	Any	Yes or No	PD
Any	PD	Yes or No	PD
Any	Any	Yes	PD

Note: Patients with a global deterioration of their health status requiring discontinuation of treatment without objective evidence of disease progression at that time should be classified as having "symptomatic deterioration." Every effort should be made to document objective progression, even after discontinuation of treatment.

In some circumstances, it may be difficult to distinguish residual disease from normal tissue. When the evaluation of complete response depends on this determination, it is recommended that the residual lesion be investigated (fine needle aspirate/biopsy) before confirming the complete response status.

